6.4 Interventions - Arm A and Arm B

All patients will attend the secondary care clinic for fortnightly visits or as per current standard care, outlined in 6.4.5. Additional visits maybe arranged depending on clinical need. Procedures which are part of standard care will be completed according to trial specific WPD.

In this trial a standardised assessment of serial temperature measurements will be carried out. This will be completed according to trial WPD. The temperature of both feet will be recorded at intervals of 5 minutes starting at the initial removal of the off-loading device for up to 15 minutes. This will assess acclimatisation and the period of equilibration needed for stabilisation of temperature.

- 1) Following initial removal of the off-loading device
- 2) Following a 5 minute resting period
- 3) Following a 10 minutes resting period
- 4) Following a 15 minutes resting period

The sites where the temperature will be recorded reflect the current classification tool developed by Sanders and Frykberg⁴⁸;

1. distal and proximal interphalangeal joints, metatarsophalangeal, tarsometatarsal joints
2. naviculo-cunieform joints, talo-navicular joint
3. calcaneocuboid joint
4. ankle joint, subtalar joint
5. calcaneus

One X-ray will be additional to standard care this will be taken 6 months post remission. Participants who do not reach this time point within the 18 month intervention and follow-up period will not have this X-ray. This will enable the progression of foot deformity to be assessed. If a participant becomes pregnant during the study they will not have the additional X-ray and will be excluded from the analysis of the progression of foot deformity. Two members of the research team will independently evaluate the images to assess the progression of foot deformity. Inter-rater reliability will be assessed. The X-rays will be anonymised prior to evaluation to ensure the researcher is blinded to participant number and site. [The anonymised scans will also be randomly sequenced to avoid bias.](#)

To allow comparison all X-ray and MRI images will be taken as per trial WPD.

The participants will also be asked to complete the following questionnaire/assessments. These will be completed at randomisation, 3 monthly until remission (3, 6, 9 and 12 months), 1 month after remission, and at 6 months post remission;

- 1) Pain in the foot and/or leg measured using a numerical 0-10 visual analogue scale

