6.4.2 Arm B (Control – Standard Care and one additional MRI)

Immobilisation discontinued on the basis of clinical remission determined by skin temperature measurement and MRI. In the standard care arm participants will receive one additional MRI when the temperature measurements, X-ray and/or signs and symptoms indicate to the clinical team that the foot is in remission.

A temperature difference of $\leq 2^{\circ}\text{C}$ which is maintained or improves on two separate consecutive occasions for a period of ≥ 4 weeks will be the indicator to arrange the second MRI, to confirm the diagnosis of remission.

If participants in either arm of the trial have not reached remission at the end of the 12 month active phase of the study they will exit the study. Ongoing standard care will be provided by their clinical team.

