6.5.3 Patient Reported Outcome Measures

The following outcomes will be collected at randomisation, and three monthly until patient is in remission. They will also be collected 1 month and 6 months post remission:

- Pain in the foot, ankle or leg measured, using the Numeric Pain Rating Scale.
- Health related quality of life assessed by the Medical Outcomes Short-Form Health Questionnaire (SF12)
- Psychological health status measured using the Hospital Anxiety and Depression Scale (HADS)
- EQ-5D-5L
- Economic Evaluation – Reported through a patient diary

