6.7.3 At three, six, nine and 12 months

In addition to standard care the following questionnaires will be administered to participants in both trial arms. Health related quality of life assessed by the SF-12, Psychological health status measured using the HADs and the EQ-5D-5L. Participants will also be asked to complete a VAS to assess the pain they have experienced in their foot, ankle or leg over the last 3 months. The three monthly assessments will only continue until the patient is in remission. Once the patient is in remission they will move to the follow up phase of the study.

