6.11.4.2 Study Outcomes

Feasibility measures

- Number of eligible patients recruited, recruitment and retention levels, willingness of clinicians to participate in the study, and dropout rates.

Efficacy outcomes

- Days with immobilisation, for the intervention versus standard care will be measured
- Number of foot ulcers, infections, falls, minor and major amputations from randomisation to the end of the study
- Progression of foot deformity from randomisation – remission, and at the end of the study.
- Changes in psychological health status assessed by the Hospital Anxiety and Depression Scale (HADS) from baseline at, 3, 6, 9 and 12 months, remission and at the end of the study period.
- Changes in health related quality of life assessed by the Medical Outcomes Short-Form Health Questionnaire (SF12) from baseline at, 3, 6, 9 and 12 months, remission and at the end of the study period.
- Changes in reported pain experienced in the foot, ankle or leg as reported on a Visual Analogue Scale (VAS) from baseline at, 3, 6, 9 and 12 months, remission and at the end of the study period.

Economic Evaluation of resource use

- Collected through a patient diary

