6.11.5 Analysis Population and Missing Data

The exploratory efficacy analyses will be on the 'Intention-to-treat' population, i.e. as per randomisation rather than intervention actually received. There are no plans to impute missing data, i.e. these analyses will be on a 'complete case' basis.

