6.11.5.1 Economic evaluations

This will explore the feasibility of collecting resource use and quality of life data, to inform the design of the health economics component of a future definitive trial.

Estimation of cost-effectiveness, within a health-technology assessment, is an iterative process⁴⁹. In this trial we aim to monitor levels of resource-use and quality of life (QoL), to inform the decision as to how costs and benefits should be measured as part of a future, more definitive study.

NICE guidance⁵⁰ recommends that costs are calculated from the perspective of the NHS and personal social services (PSS). However, it is acknowledged that not all cost data can be collected, and it is suggested that the focus be on large cost drivers and those costs that are likely to differ between arms⁵¹. We will thereby seek to monitor levels of resource-use associated with the intervention and standard care arm of the study.

Intervention - Serial use of MRI at 3, 6, 9 and 12 months to identify disease resolution and thus discontinue immobilisation

Standard Care - Immobilisation discontinued on the basis of clinical remission determined by skin temperature measurement

Data on other primary, and secondary care visits and admission to hospital will be collected. This information will be extracted using a patient diary and secondary care notes. Time off work and levels of informal care will also be monitored. Appropriate unit costs will subsequently be attached to all items of resource-use⁵².

In line with guidance⁵⁰ the EQ-5D-5L⁵³ will be used to measure quality of life (QALY (Quality Adjusted Life Year) scores can be calculated from the EQ-5D⁵⁴. Participants will be asked to complete the EQ-5D-5L at 3 months, at 6 months, 9 months, 12 months, 1 month after remission, and at 6 months post remission

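### Questionnaires stop at remission but change is planned at 3, 6, 9 and 12 months, so the later comparisons, above all month 12, are selected on a post-randomisation outcome

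*Protocol*

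**What the plan says.** Three places in the Protocol give one schedule tied to clinical phase. Section 6.4 asks for the questionnaires at randomisation and "3 monthly until remission (3, 6, 9 and 12 months), 1 month after remission, and at 6 months post remission". Section 6.5.3 has them "collected at randomisation, and three monthly until patient is in remission", and 6.7.3 states the limit outright: "The three monthly assessments will only continue until the patient is in remission". Section 6.7.4 confirms that, once remission is reached, full sets are due only at follow-up months 1 and 6.

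Two places read differently. Section 6.11.4.2 plans change in HADS, SF-12 and pain "from baseline at, 3, 6, 9 and 12 months, remission and at the end of the study period", with no restriction to people still in the active phase. Section 6.11.5.1 says "Participants will be asked to complete the EQ-5D-5L at 3 months, at 6 months, 9 months, 12 months, 1 month after remission", and again at 6 months post remission, also without the limit.

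Three further statements bear on this:
- Section 6.11.5 calls the exploratory efficacy analyses intention-to-treat and adds "There are no plans to impute missing data".
- Section 6.4.2 says that participants in either arm who "have not reached remission at the end of the 12 month active phase of the study they will exit the study".
- Section 6.11.5.2 plans a mean incremental cost and a mean QALY gain between arms.

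**The concern.** A month-6, -9 or -12 set exists, in the main, only for someone not yet in remission. Remission happens after randomisation, and the intervention aims to bring it forward. A complete-case comparison at those months is therefore conditioned on the outcome under study, whatever the intention-to-treat label says. It compares whoever happens to have a set in each arm.

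The end-of-study measure does not repair this. It falls 6 months after remission for remitters and at month 12 for those who exit without remission, so it too comes at a time set by the outcome. A set taken at remission itself would not fill the later months either.

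The gap lies in collection. A later analysis plan can choose other time points or a shorter QALY window, but it cannot recover questionnaires that were never given. Feasibility of collecting quality-of-life and resource data is itself a listed outcome (6.5.1), and 6.11.5.2 will estimate completion rates to inform a definitive trial. While the sections disagree, the number of sets due at 6, 9 and 12 months is unclear, and so is the denominator of those rates.

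**Working it through.** The plan states no figure to reproduce; the sample of 60 is not derived from a calculation. The check follows individual participants first and then illustrates the numbers. R is the month of remission.

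**Individual schedules**
- A control with R = 4 has sets at 0, 3, 5 (R+1) and 10 (R+6), and none at 6, 9 or 12.
- An Arm A participant with R = 3 has sets at 0, 3, 4 and 9, and none at 6 or 12.
- An Arm A participant with R = 6 has sets at 0, 3, 6, 7 and 12, and none at 9.
- An Arm A participant with R = 9 has sets at 0, 3, 6, 9, 10 and 15, and none at 12.

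**Inputs**
- From the Protocol: 30 per arm (6.8), UK median time to remission 9-12 months (5.1), Arm A scans at 3, 6, 9 and 12 months (6.4.1).
- Assumed: paired Arm A/control medians of 6/9, 7.5/10.5 and 9/12 months; Weibull shape k = 1, 1.5, 2 or 3; no dropout; Arm A remission dated to the next scan; control remission at any time.

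Proportion not in remission by month t with median m: S(t) = 0.5^((t/m)^k).

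**Control sets at exact times: 30 × S(t)**
- Month 6: from 30 × 0.5^(6/9) = 18.9 to 30 × 0.5^((6/12)^3) = 27.5.
- Month 9: 15 (median 9) to 22 (median 12, k = 3).
- Month 12: 15 with median 12 for every k; 11.9 with median 9 and k = 1; 5.8 with median 9 and k = 3. Range 6-15.

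That at least half lack the month-12 set needs only a median of 12 months or less, not the Weibull shape.

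**Arm A at month 12.** Write p3, p6, p9 and p12 for remission declared at each scan and pn for none by month 12. Sets present = 30 × (p6 + p12 + pn). With median 6 and k = 1: p3 = 0.293, p6 = 0.207, p9 = 0.146, p12 + pn = 0.354, giving 30 × 0.561 = 16.8. Range over all scenarios 15-21.

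**Controls at month 12 with a window of 1 month either side** (the Protocol gives no window). A set is regained if R+1 or R+6 falls between months 11 and 13, so R in 10-12 or 5-7. With median 9 and k = 1: (0.463 − 0.397) + (0.680 − 0.583) = 0.163, or 4.9 of 30. Earlier remitters number 30 × (1 − 0.397) = 18.1, so 13.2 of 18.1 (73%) still lack a set. With median 12 and k = 3, 7.5 of 15 are regained and 50% still lack one. Range 50-73%.

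**EQ-5D-5L coverage.** Under the stop rule, collection ends before month 12 for anyone remitting before month 6: 30 × (1 − S(6)) = 2-11 controls, and 30 × p3 = 1-9 in Arm A. Only 0.3-6 controls remit before month 3, so 24-30 of 30 are covered to month 9, as is all of Arm A.

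**The case against.** **The conflict may be shorthand.** Section 6.4 itself puts the four months in brackets after the remission limit, and 6.11.5.1 also omits the randomisation set that other sections require, which suggests an abbreviated list. This is a fair reading, and one added clause would cure the wording. It would not cure the selection: if the months apply only to people not in remission, the comparisons at those months are restricted by outcome on purpose.

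**Remitters are not unmeasured, and burden was limited deliberately.** Both stand. Section 6.11.4.2 also names remission and end of study, and 6.7.8 and 6.9.2 explain the visit pattern. But remission-anchored sets answer a different question from change at a common time since randomisation.

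**A reader might go further and infer a known imbalance between arms.** Arm A remission follows a 3-monthly scan and control remission a temperature trigger, so on exact dates the 6-month post-remission set of an Arm A month-6 remitter lands on month 12, while control remitters generally have nothing there. The documents do not support a definite imbalance:
- At month 9, the timeline in 6.6 puts month 3 at week 12 and month 9 at week 40. Six months after week 12 is about week 38, so counting that set gives Arm A a tolerance withheld from controls. Allowing 2 weeks either side for controls too, the arm difference in the share of sets from people already in remission is −8 to +20 percentage points.
- At month 12, with 1 month either side, it is −9 to +16 points.
- Section 6.7.2 lets remission rest on MRI and/or clinical signs and asks for scans to coincide with visits only where possible, so Arm A remission need not fall on scan days.

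**Consequences are modest.** Between-group analyses are exploratory (6.11.4.1), and 6.11.5.2 itself urges caution about cost-effectiveness. This limits the weight of the point but does not remove it.

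**Conclusion.** The point holds. As written, the month-6, -9 and -12 comparisons, and month 12 above all, depend on remission and are not comparisons of the arms as randomised. If control remission follows the cited UK median of 9-12 months, at least half of controls have no set scheduled at exactly month 12. With an assumed window of 1 month either side, about 50-73% of control earlier remitters still have none. A control median above 12 months would reduce the loss.

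The loss may differ by arm because the routes to remission differ, but neither its size nor its direction is established. Both depend on assumed remission times and visit windows.

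Days with immobilisation, the suggested primary efficacy outcome, is unaffected. No QALY horizon is fixed, and a 9-month window would be covered for all of Arm A and most controls, so the effect on the preliminary QALY estimate may be small. This is a worthwhile, cheap correction to an exploratory part of a feasibility trial, valuable mainly because the collection schedule is one of the things being tested.

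**What to change.** In 6.4, 6.5.3, 6.6, 6.7.3 and 6.11.5.1, schedule EQ-5D-5L, SF-12, HADS and pain at 0, 3, 6, 9 and 12 months from randomisation for every participant who has not withdrawn or exited, regardless of remission. Use existing follow-up visits where they fall close; a control with R = 4 already attends at month 6, for example. Otherwise use post or phone, and record the mode. Keep the sets at 1 and 6 months after remission, counting one set where they coincide with a fixed time within a stated window. Continue resource-use collection to month 12 for all; 6.11.5.1 already names two sources ("This information will be extracted using a patient diary and secondary care notes"). Calculate costs and QALYs over one common window.

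**Cost**, under the assumptions above, crediting the 6-month post-remission set of Arm A month-3 and month-6 remitters to months 9 and 12:
- Arm A: 30 × (2 × p3 + p6 + p9) = 16-30 extra sets.
- Control: 30 × [(1 − S(3)) + (1 − S(6)) + (1 − S(9)) + (1 − S(12))] = 25-50.
- Total by scenario: 15.8 + 25.4 = about 41 (medians 9/12, k = 3) to 28.2 + 50.4 = about 79 (medians 6/9, k = 1), or roughly one set per participant.

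If the stated window is too narrow to credit month-3 remitters at month 9, add 1-9 sets. There would also be some further diaries, and some difference in mode of collection tied to remission. The trial need not be extended, since 6.7.9 ends it 18 months after the last consent.

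**At minimum**, reconcile 6.11.4.2 and 6.11.5.1 with 6.4, 6.5.3 and 6.7.3, and do not present month-6, -9 and -12 results as intention-to-treat comparisons.

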6.7.4 Follow up phase

In both arms once remission is confirmed by the MRI patients will then enter a rehabilitation/weaning phase. They will be transferred into a less restrictive off-loading device and then finally into footwear as per standard care. Participants will continue to attend for monthly trial visits for 3 months to monitor for any sign of relapse. The final visits will be at 6 months post remission. Standard care will continue to be provided.

At each visit study specific procedures will be carried out:

- The temperature will be assessed as per the WPD
- The participant diary will be collected and another issued for participants to complete until their next study visit. (This is only for the first three follow-up visits)

In addition to standard care and study specific procedures the participant will be asked to complete the following questionnaires and additional tests/investigations:

Follow Up - Month 1: VAS, SF-12, HADS and EQ-5D-5L will be completed.

Follow UP Month 6: VAS, SF-12, HADS and EQ-5D-5L completed. BMI will be recorded and an X-ray of the foot and/or ankle will be taken.

Relapse will be defined as a temperature difference of $>2^{\circ}\text{C}$ compared to the contralateral foot maintained for two or more occasions or further changes on imaging¹⁵. As per standard care the final decision as to whether the participant has relapsed will be at the discretion of the clinic team. If this occurs, then the participant will then recommence off-loading with a non-removable device. They will continue to be followed up as per the study protocol.

6.7.5 Alternate Diagnosis

The diagnosis of CN can sometimes be difficult, and a confirmed diagnosis may take several weeks to reach. As per standard care all participants will be treated for CN until it is proven otherwise. If during the course of the trial the clinical team treating the participant decide on an alternative diagnosis then the participant will exit the study. Follow-up care will be provided by the appropriate clinical team.

6.7.6 Early Stopping of Follow-up

If a participant chooses to discontinue their trial treatment, they should continue to be followed up as per current standard care. This will be as close as possible to the follow-up schedule defined in the protocol, providing they are willing. They should be encouraged and facilitated not to leave the whole trial, even though they no longer continue with the trial treatment. If, however, the participant exercises the view that they no longer wish to be followed up either, this view must be respected and the participant withdrawn entirely from the trial. NCTU should be informed of the withdrawal in writing using the appropriate CADOM trial documentation. Data already collected will be kept and included in analyses according to the intention-to-treat principle for all participants who stop follow up early.

Participants who stop trial follow-up early will not be replaced.

6.7.7 Participant Transfers

If a participant moves from the geographical area, making continued follow up at their consenting centre inappropriate, then it will not be appropriate for the patient to continue in the trial.

6.7.8 Loss to Follow-up

Contact details will be stored in the patient records and usual hospital procedures will be used to contact the patient about follow up visits. If this is without success, the patient will be recorded as lost to follow up. Number of patients where this has occurred will be monitored by the TMG. CN patients are normally seen at least fortnightly during the treatment period and monthly during the first 3 months remission period as part of routine care. Six month follow-up visit will be scheduled with participants during a three month visit. The trial has been designed in line with clinical practice to reduce the burden on participants and therefore the number of participants lost to follow-up

6.7.9 Trial Closure

The end of the trial is defined as 18 months after the final patient consents to take part in the study

6.8 Sample Size

As this is a preliminary, feasibility study a power calculation is not required. The sample size will be limited to 60 patients with 30 participants per arm. This number has been chosen based on guidelines from the NIHR and Research for Patient Benefit guidance.

6.9 Recruitment and Retention

6.9.1 Recruitment

Recruitment will be across two sites Norfolk & Norwich Hospital and Derby Hospital. It is anticipated the identified trial centres will be able to recruit 60 patients over an 18-month trial period. If recruitment is below the level anticipated, recruitment may be extended to additional sites.

Clinicians working in the diabetic foot clinics identified for the trial will be asked to identify potential patients. They will make an assessment of the patient's eligibility to join the trial and provide the patient information to prospective patients.

One of the outcomes of the feasibility trial is to assess recruitment and retention, to inform a full scale RCT if warranted.

6.9.2 Retention

Discussion with patients and other PPI representatives, prior to the development of this proposal showed a willingness to participate in the trial. They did not feel the visit schedule was overly burdensome as the majority of visits would be carried out at the same time as their routine clinical appointments. A regular six monthly newsletter will be sent out to all participants.

6.10 Assignment of Intervention

6.10.1 Allocation

Randomisation will take place after the patient has consented to participate in the trial

6.10.1.1 *Sequence generation*

Eligible consented participants will be randomised on a 1:1 basis to one of the two trial arms using a web based randomisation process. The randomisation scheme will be generated by the NCTU data manager and notified by email to the study team. Allocation will be stratified by centre.

6.10.1.2 *Allocation concealment mechanism*

The allocation is computer generated so will not be known prior to the participant being randomised. The patient will be allocated a participant number at time of consent. When confirmation of the diagnosis of CN has been entered, and all other pre-designated questions completed in the CRF, the research staff will then have access to the randomisation process for that participant. The treatment allocation will be revealed and linked to that participant number. Allocation is concealed prior to randomisation to prevent treatment bias.

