Key Inclusion and Exclusion Criteria	
Target population: NHS patients with type 1 or type 2 diabetes and a diagnosis of new or suspected acute Charcot neuroarthropathy
 
Inclusion Criteria:
 
 • Participants who are willing and have capacity to give informed consent. • People with diabetes as diagnosed by the WHO criteria (Appendix 1) http://www.who.int/diabetes/publications/diagnosis_diabetes2011/en/ • Age 18 years or over • New or suspected new diagnosis of acute CN (no previous incidence of acute CN within the last 6 months on the same foot) treated with off-loading • Understand written and verbal instructions in English 
Exclusion Criteria:
 
 • People who have received a transplant and other patients receiving immunosuppressant therapy or using long term oral glucocorticoids other than in the routine management of glucocorticoid deficiency. Participants on a low doses of oral glucocorticoids (<10mgs for ≤7 days) are eligible to participate in the study. • Participation in another intervention study on active CN • Contra-indication for MRI • Treatment for previous suspected CN on the same foot in the last 6 months • Suspected or confirmed bilateral active CN at presentation • Active osteomyelitis • Previous contralateral major amputation • Inability to have an MRI scan • Patients receiving palliative care
Study Type	A multicentre, open labelled, two arm randomised controlled feasibility trial
Date of First Enrolment	September 2017
Target Sample Size	60
Feasibility Outcomes	
 • The proportion of patients who meet the eligibility criteria • The number of eligible patients recruited • The number of participants in which an alternative diagnosis is made during the active phase of the trial • The proportion of patients that withdraw or are lost to follow up. The term 'withdrawal' encompasses two potential scenarios; withdrawal due to loss of consent or withdrawal due to death • Statistical parameters of the key outcome measures to inform a sample size calculation for a definitive trial (estimate of effect size) • Ability to collect quality of life and resource use data
Exploratory Analysis of	
Efficacy Outcomes
 
 • Preliminary data on days with immobilisation

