6.1.1 Study Setting

Participants will be identified at the point of a suspected diagnosis of CN from two diabetic foot clinics based in secondary care in the UK. Initially the collaborating centres identified will be the Norfolk and Norwich University Hospitals NHS Foundation Trust and Derby Hospitals NHS Foundation Trust. As the study progresses the involvement of other centres will be considered, as necessary to meet the recruitment target.

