6.3.1.1 Participant selection

There will be **NO EXCEPTIONS** (waivers) to eligibility requirements at the time of randomisation. Questions about eligibility criteria should be addressed PRIOR to attempting to randomise the participant.

The eligibility criteria for this trial have been carefully considered and are the standards used to ensure that only medically appropriate participants are entered. Participants not meeting the criteria should not be entered into the trial for their safety and to ensure that the trial results can be appropriately used to make future treatment decisions for other people with similar diseases or conditions. It is therefore vital that exceptions are not made to these eligibility criteria.

Participants will be considered eligible for enrolment in this trial if they fulfil all the inclusion criteria and none of the exclusion criteria as defined below.

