6.3.1.2 Participant Inclusion Criteria

- Participants who are willing and have capacity to give informed consent.
- People with diabetes as diagnosed by the WHO criteria
http://www.who.int/diabetes/publications/diagnosis_diabetes2011/en/
- Age 18 years or over
- New or suspected diagnosis of acute CN (no previous incidence of acute CN within the last 6 months on the same foot) treated with off-loading
- Understand written and verbal instructions in English

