6.6 Participant Timeline

	Active Phase (fortnightly visits throughout active phase of trial)										Remission	Follow Up after remission diagnosed			
Visit Number	1		6		11		18		25			FUV1	FUV2	FUV3	FUV4
month			3m		6m		9m		12m			1month	2months	3months	6months
Week **	0	2 weekly	W12	2 weekly	26	2 weekly	40	2 weekly	52						
Check In/exclusion criteria *	*														
Hand out FIS *	*														
Consent *	*														
Randomisation *	*														
Medical History *	*														
Foot Surgical history *	*														
Medication *	*	*	*	*	*	*	*	*	*	*	*	*	*	*	*
Record any amputation/s *	*	*	*	*	*	*	*	*	*	*	*	*	*	*	*
Record any infection/s *	*	*	*	*	*	*	*	*	*	*	*	*	*	*	*
Record any ulceration/s *	*	*	*	*	*	*	*	*	*	*	*	*	*	*	*
Record any falls *	*	*	*	*	*	*	*	*	*	*	*	*	*	*	*
Hand out patient diary *	*	*	*	*	*	*	*	*	*	*	*				
Collect & upload diary *		*	*	*	*	*	*	*	*	*	*				
Foot temperatures *	*	*	*	*	*	*	*	*	*	*	*	*	*	*	*
MRI (usual care) **	*									*					
MRI (Intervention arm) **	*		*		*		*		*						
Classification *	*														
Neuropathy Assess *	*														
Vascular Assess *	*														
BMI *	*		*		*		*		*		*				*
HbA1c (use existing if <3months) *	*														
Pain VAS *	*		*		*		*		*		*				*
HADS *	*		*		*		*		*		*				*
SF-12 *	*		*		*		*		*		*				*
EQ5D *	*		*		*		*		*		*				*
Study specific X-ray															*
		← Duration of active phase of treatment will be variable →													
Patient Interviews		← →													

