6.7.1 Randomisation Visit

These visits will take place in secondary care clinics.

Standard Care

- The off-loading device will be provided, if one has already been provided it will be removed and the foot/leg checked for any problems
- Assessment of neuropathy using the 10g monofilament and neurotheisometer

- Palpation of foot pulses
- Measurement of ABPI
- BMI recorded
- Measurement of HbA1c if not previously tested in the last 3 months
- Skin and nail care treatment given as necessary
- Treatment of any underlying wounds, ulceration and/or infection
- The off-loading device will be re-applied

Standard Care (Plus) – these tests and investigations are part of standard care but will be carried out according to trial WPDs. This will ensure standardisation across the site.

- X-ray of the affected foot
- MRI of the affected foot
- Foot temperature assessment

Study Specific Procedures

- The following questionnaires will be administered;
 - Health related quality of life assessed by the Medical Outcomes Short-Form Health Questionnaire (SF12)
 - Psychological health status measured using the Hospital Anxiety and Depression Scale (HADS)
 - EQ-5D-5L
- Participants will also be asked to complete a VAS to assess the pain they have experienced in their foot, ankle or leg over the last two weeks
- At each visit a patient diary will be issued and participants asked to complete it recording other visits to health care professionals. It will then be collected at the next visit and another one issued.

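### Does the randomisation gate's call for a confirmed diagnosis of CN shut out the suspected cases that the protocol makes eligible?

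*Protocol*

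**What the plan says.** Section 6.10.1.2 (Allocation concealment mechanism) gives the participant a number at consent and unlocks randomisation "When confirmation of the diagnosis of CN has been entered, and all other pre-designated questions completed in the CRF". It does not say what counts as confirmation. Section 6.10.1.1, directly above it, says that "Eligible consented participants will be randomised on a 1:1 basis".

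On who is eligible, section 1.3 lists "New or suspected new diagnosis of acute CN" and section 6.3.1.2 lists "New or suspected diagnosis of acute CN". Section 6.1.1 adds that "Participants will be identified at the point of a suspected diagnosis of CN". Section 6.3.1.1 allows no waivers to "eligibility requirements at the time of randomisation".

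Section 6.7.5 says that CN can be hard to diagnose and may take several weeks to confirm. Participants are meanwhile managed as having CN unless it is disproved, and they leave the study if another diagnosis is made. Section 6.5.1 makes the number of such alternative diagnoses a feasibility outcome, alongside the number of eligible patients recruited.

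**The concern.** The protocol seems to set two thresholds for entry. The inclusion criteria admit suspected disease; the gate in section 6.10.1.2 appears to want confirmed disease. Section 6.7.5 sharpens the contrast, because there a confirmed diagnosis is something that may arrive only after weeks. The schedule in section 6.6 puts "Check In/exclusion criteria", consent, randomisation and the baseline MRI in one week-0 column, which seems to leave no room for waiting.

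At stake would be two outcomes that a feasibility trial exists to measure. Under a literal gate, the number of eligible patients recruited could omit people who satisfy every criterion, and the alternative-diagnosis count would cover only confirmations that proved mistaken. Under a looser gate, the same count would show how often new or suspected CN turns out to be something else. If sites differed in how they applied the gate, neither figure would be easy to use in planning the definitive trial.

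**Working it through.** There is no figure to reproduce. Section 6.8 sets 60 participants (30 per arm) from funder guidance without a power calculation, and nothing in the concern depends on that number. The check is a comparison of the two readings against each relevant section.

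| Section | Literal reading: CN must be confirmed | Softer reading: the CRF records that the diagnostic criterion is met |
|---|---|---|
| 6.10.1.1, eligible and consented patients are randomised | Conflicts: an eligible, consented, suspected case would wait or be lost | Fits |
| 1.3 and 6.3.1.2, suspected CN is eligible | The word suspected has no effect at randomisation | Fits |
| 6.1.1, identification at suspicion | Possible, with a wait before randomisation | Fits |
| 6.3.1.1, no exceptions to the criteria | Adds a condition that is not in the list | The gate checks the list |
| 6.7.5, managed as CN unless disproved; exit on another diagnosis | Needed only for mistaken confirmations | A natural provision for unconfirmed cases |
| 6.5.1, alternative diagnoses as an outcome | Of little interest | Informative |
| 6.10.1.2, the entry stands beside the other CRF questions | Possible | Fits: one CRF item among several |
| 6.7.5, confirmed used of a later state | Fits | Some strain on the vocabulary |

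The softer reading agrees with the substance of every section and strains only the choice of word. The literal reading conflicts with sections 6.10.1.1, 6.3.1.2 and 6.3.1.1.

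**Timing.** The shared week-0 column does not show that all diagnostic work must follow consent. Section 6.3.1.6 allows standard-care procedures before consent. Section 6.7.1 classes the X-ray, the "MRI of the affected foot" and the foot temperatures as standard care done to trial working documents, and it refers to visits in the plural. Some of the work-up can therefore come before the patient reaches the gate. A column in a schedule also does not prove that consent and randomisation fall on the same day.

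**Effect on the outcomes.**
- *Recruited count.* Delay alone does not remove a patient from this count; only failure to be randomised does. Nothing in the protocol suggests that suspected cases were meant to be left out.
- *Alternative-diagnosis count.* Its meaning does depend on the reading. Under the reading that fits the other sections, it measures what the protocol appears to want.
- *Comparison of arms.* The gate is passed before allocation is revealed, so it acts on both arms alike.

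**Size.** The protocol gives no share of suspected cases and no time to confirmation beyond several weeks. Any figure for delay or lost recruitment would be the assumption restated, so none is offered.

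**The case for a change.** The best case for a change rests on the protocol's own vocabulary. Section 6.3.1.3 names suspected and confirmed bilateral disease as separate states, and section 6.7.5 keeps confirmed for something that may come weeks later. One site could take section 6.10.1.2 at its word while another randomised suspected cases under section 6.10.1.1, and both could say they followed the protocol. The screening and enrolment logs in section 6.11.1 might show who was held back, but a patient never randomised cannot enter an outcome that counts participants in the intervention phase. The remedy would be cheap: one sentence and one database field.

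Part of this stands. The term is not defined in the protocol, and a record of suspected or confirmed status at randomisation would help a reader interpret the alternative-diagnosis count. That record is a useful extra rather than the correction of an error.

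The predicted harm does not follow. It needs a site to adopt the reading that fits the other sections worse, in a trial with one web-based randomisation process (section 6.10.1.1), a central database (sections 6.11.1 and 6.11.2) and study-specific training (section 6.3.1.4). Eligibility questions must be raised before randomisation (section 6.3.1.1) and concerns go to the Chief Investigator (section 6.3.1.5). The gate question itself sits in the CRF, which is not among the documents at hand and is the natural place for the exact wording.

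**Conclusion.** The tension in wording is real, but it is missing detail and no change to the plan is called for. The protocol says who is eligible, says that eligible and consented patients are randomised, and provides for participants whose diagnosis later changes. Against that background, confirmation in section 6.10.1.2 is sensibly taken as a CRF entry that the new-or-suspected criterion is met. Nothing here chooses a diagnostic standard; that stays with the trial team.

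No effect on any result has been shown, and none can be calculated from the protocol. Between-arm bias is not in question, because the gate comes before allocation. The efficacy analyses are in any case exploratory (section 6.11.4.1).

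The conclusion assumes that the database question agrees with the listed eligibility criteria and is the same at every site. If the CRF did demand proven CN, the concern would have substance, and the recruitment and alternative-diagnosis figures would have to be reported with that stated.
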